2. OBJECTIVES AND STUDY PURPOSE

Based on the strong preclinical evidence from our laboratory and others, ***our primary hypothesis is that oral administration of VSL#3 is a feasible, well-tolerated and effective strategy to prevent bone loss in postmenopausal women.*** We further hypothesize that this simple approach will favorably impact biomarkers relevant to bone turnover, including inflammatory and osteoclastogenic cytokine production.

Specific Aim 1. To conduct a placebo-controlled, double blind, prospective clinical trial in which the commercially available oral probiotic VSL#3 will be administered to otherwise healthy, postmenopausal women for 12 months. The primary objective will be to demonstrate that VSL#3 administration safely maintains or improves bone density in the lumbar (L1-L4) spine, femoral neck, and total hip area in the study subjects at 1 year.

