Study drug tolerance will be assessed by obtaining serial measures of the Gastrointestinal Symptom Rating Scale (GSRS) every two weeks during the 12-month placebo or probiotic regimen²¹. These will be obtained with in-person interviews at the baseline and month 6 and 12 visits and by telephone contact with all subjects by the study coordinator every 2 weeks. Data will be analyzed within the 5 symptom domains depicting symptoms related to gastric reflux, abdominal pain, indigestion, diarrhea, and constipation. A GSRS total score, the sum of all 5 domains, will also be assessed. To our knowledge there is no published absolute or change in the GSRS score that is demonstrative of intolerance to a study drug or other treatment²¹⁻²³. Therefore we will *a priori* define intolerance to the study drug as a 50% increase in the total GSRS score from baseline at any two consecutive time points, or the new onset of a GSRS classifier score of 2 or 3 in at least three of the 15 gastrointestinal symptoms queried. If either of these signs of intolerance occurs, we will offer the subject the options of: 1) discontinuing from the study; 2) discontinuing the study drug but participating in the serial assessments (e.g. blood draws, DXA) in the research center, or 3) decreasing the dose of blinded study drug to one sachet/daily, with the option of resuming the two sachet/day study regimen upon resolution of symptoms. If intolerance symptoms recur, the same strategy will be followed. All episodes of intolerance to study drug and the twice-monthly GSRS data will be recorded by the study coordinator in the individual subject case report forms (CRFs) (see below).

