4.14. Statistical analyses: Demographic data will be summarized with standard descriptive statistics. Repeated-measures analyses for each outcome (i.e., GSRS scale scores, BMD) will be performed with a means model via the SAS MIXED Procedure (version 9.4; SAS Institute, Cary, NC), providing separate estimates of the means by time on study (baseline, 1-year and 2-years) and treatment group. The model will include three predictors (treatment arm, time on study and the statistical interaction between treatment arm and time on study). A compound-symmetric variance-covariance form in repeated measurements will be assumed for each outcome and robust estimates of the standard errors of parameters will be used to perform statistical tests and construct 95% confidence intervals²⁴. The model-based means are unbiased with unbalanced and missing data, so long as the missing data are non-informative (missing at random, MAR). A P-value ≤0.05 will be considered statistically significant for the main effects (treatment and time on study) and for the treatment by time on study interaction effect from the repeated measures analysis. The statistical test for interaction between time on study and treatment will be the primary overall hypothesis test to determine whether an outcome in the two study groups changed in significantly different ways during follow-up (i.e., different temporal patterns over time). If a mean outcome in the two groups is consistently different or similar over time (i.e., no statistical interaction) then the main effect test for treatment will be used as the primary test of VSL#3 efficacy. If a significant interaction is detected, then t-tests will be used to compare the differences between the model-based intervention means at each time point and to compare differences over time within each treatment arm. Specific statistical tests will be done within the framework of the mixed effects linear model. Analyses will control for risk factors for osteoporosis, such as age, gender, race, BMI, habitual alcohol consumption, smoking, physical activity, and fracture history, as necessary. All tests will be 2-sided and a P value ≤ 0.05 will be considered significant.

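### Tolerability is analysed only through mean GSRS, although the protocol defines and records intolerance and adjusts dose for it; the proportion of women intolerant is never compared between arms

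*Combined protocol and SAP*

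**What the plan says.** Section 2 makes tolerability part of the primary hypothesis: oral VSL#3 is to be a "feasible, well-tolerated and effective strategy to prevent bone loss in postmenopausal women". Section 4.9 makes change in lumbar spine BMD the primary endpoint, so tolerability has no endpoint of that rank.

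Section 4.10 has GSRS collected every two weeks for 12 months, about 26 contacts after baseline. It defines intolerance in advance by either of two criteria: a 50% rise in total score over baseline at two contacts in a row, or new scores of 2 or 3 on at least three of the 15 symptoms. A woman who meets either is offered three choices: leave the study, stop the drug but stay for assessments at the centre, or "decreasing the dose of blinded study drug to one sachet/daily, with the option of resuming the two sachet/day study regimen upon resolution of symptoms". The section adds that "All episodes of intolerance to study drug and the twice-monthly GSRS data will be recorded by the study coordinator".

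Section 4.14 then states: "Repeated-measures analyses for each outcome (i.e., GSRS scale scores, BMD) will be performed with a means model", giving "separate estimates of the means by time on study (baseline, 1-year and 2-years) and treatment group". On the order of tests it says "The statistical test for interaction between time on study and treatment will be the primary overall hypothesis test"; without an interaction, "then the main effect test for treatment will be used as the primary test of VSL#3 efficacy". It mentions neither intolerance episodes, dose reductions nor drug stops, and does not say how GSRS scores after a dose change are treated.

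**The concern.** The score being analysed is also the score that triggers a change in treatment. If a woman's symptoms settle once she halves or stops the product, her later scores return towards baseline, and her intolerance shows only at the contacts before the change. A comparison of means then measures symptoms among women many of whom may no longer be on the assigned regimen. That is a legitimate quantity, but it does not tell the reader how many women could not take two sachets a day.

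The protocol already defines that outcome and collects it. Without a planned between-arm comparison, the main quantitative evidence on the well-tolerated part of the hypothesis would be a test that can be insensitive to it. The named time points make this worse: a 2-year mean cannot exist in a 12-month trial, and a month-12 mean says little about an episode that resolved in the first months.

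**Working it through.** **The plan's own power figure.** The only one is for BMD: difference 0.03 g/cm², SD 0.03, 20 per arm, two-sided 5%. It reproduces: 88.5% by normal approximation and 86.9% by noncentral t with 38 df, against a stated figure above 85%. There is no figure for GSRS or intolerance.

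**Inputs.** From the documents: 20 per arm, about 26 post-baseline contacts, two-sided 5%, compound symmetry, interaction tested first. Assumed, because the documents give none: baseline GSRS 6 points, between-woman SD 3, within-woman SD 2, a 6-point rise during an episode, and intolerance in 40% on VSL#3 versus 5% on placebo.

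**Step 1: dilution of the year mean.** If the rise lasts k of 26 contacts and then resolves, the expected arm difference is (p1 − p0) × rise × k/26.
- k = 2: 0.35 × 6 × 2/26 = 0.16 points (7.7% of the undiluted difference)
- k = 4: 0.35 × 6 × 4/26 = 0.32 points (15%)
- k = 26: 0.35 × 6 = 2.1 points
- Half the rise persisting after 2 contacts, onset at the first contact: (2 + 24 × 0.5)/26 = 54% of the undiluted difference

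**Step 2: power of the planned tests.** 3,000 simulated trials per case, complete data, model-based standard errors (the plan uses robust ones).

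| Pattern, 40% vs 5% intolerant | Interaction, baseline and month 12 | Interaction, baseline, 6 and 12 months | Interaction, all contacts | Main effect, all contacts |
|---|---|---|---|---|
| Symptoms persist all year | 44% | 48% | 36% | 38% |
| Half the rise persists, onset in first 12 weeks | 19% | 20% | 17% | 15% |
| Resolves after 2–4 contacts, onset in first 12 weeks | 5% | 5% | 16–46% | 4–6% |
| Resolves after 2–4 contacts, all start at first contact | 5% | 5–6% | 56–75% | 6% |
| Resolves after 2–4 contacts, onset spread over the year | 5–6% | 6–7% | 5–7% | 6% |

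The test size is 5%, so entries near 5% mean no sensitivity.

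**Step 3: sensitivity to the SD.** A t-test on year-average change, with resolution after 4 contacts, has about 5–8% power if the SD of that average is 2, about 15% if it is 1, and about 38% if it is 0.5.

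**Step 4: the proportion intolerant.** Fisher exact power with 20 per arm and no misclassification:
- 30% vs 5%: 45%
- 40% vs 5%: 72%
- 50% vs 5%: 89%
- 40% vs 10%: 49%
- 50% vs 10%: 74%

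This calculation needs no GSRS SD and does not depend on symptoms persisting.

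**Step 5: false positives in the definition.** The 50%-rise criterion is checked at about 26 contacts. With a baseline of 6 and the SDs above, noise alone flags about 40% of women; with within-woman SD 1, about 20%; with a baseline of 20, under 3%. If noise flags 20% independently of true intolerance, the active rate is 1 − 0.80 × 0.60 = 52%. The placebo rate is 1 − 0.80 × 0.95 = 24%, or 20% with no true placebo intolerance. Fisher power then falls from 72% to 34–46%. If noise flags 40%, the rates are 1 − 0.60 × 0.60 = 64% versus 1 − 0.60 × 0.95 = 43% (or 40%), and power is 16–21%.

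**The case against.** The strongest reply is that the planned analysis is sound and the information is not lost. Dose adjustment is part of the protocol regimen, so mean GSRS under it is a treatment-policy measure that fits the intent-to-treat design. The choices are offered, not imposed, and apply blinded in both arms. At least one raised score, and two under the first criterion, is recorded before any action. Women who leave after raised scores are handled under missing at random, which tends to carry their elevation forward. Compliance and retention are secondary endpoints, sachets are counted, and gastrointestinal adverse events are graded under section 7.3. All of this stands, but none of it supplies a planned comparison of intolerance between arms.

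A reader might infer more than the documents support, in three ways.
- *That the rule erases the signal.* This needs symptoms to resolve after an optional dose change, and section 4.10 itself anticipates recurrence.
- *That neither planned test can detect intolerance.* The interaction test comes first and keeps real power when episodes cluster early and all contacts enter the model.
- *That a non-significant GSRS result will be taken as proof of tolerability.* No section says so.

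It is also fair that the proportion is not automatically the more powerful measure: with low baseline scores, noise in the 50% criterion can remove most of its advantage.

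**Conclusion.** The point holds as a gap in the analysis plan. Tolerability is in the primary hypothesis, intolerance is defined in advance and recorded, and the only specified GSRS analysis is of means that the dose-adjustment rule can pull together. At the named time points inside the trial, early intolerance that resolves leaves almost no signal: about 5% power at an assumed 40% versus 5%. With all biweekly contacts and early onset the interaction test keeps about 16% to 75%; with onset spread over the year it falls to 5–7%. If symptoms persist all year, the interaction has about 36–48%. The description that fits is attenuation, sometimes severe.

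Every power figure rests on assumed GSRS values, SDs and intolerance rates. The case for comparing proportions does not depend on them: it is the direct measure of whether women could take the assigned regimen.

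**What to change.** In section 4.14:
- Make the main tolerability comparison the proportion of all randomized women in each arm with a first protocol-defined intolerance episode, or a dose reduction or drug stop for intolerance (including leaving the study for that reason), by month 12. Give the risk difference, 95% CI and an exact test, or use time to first event. State how women who leave early without an event are counted.
- Report the components separately: each of the two intolerance criteria, dose reductions, and stops. This shows how much of the total could be noise in the 50%-rise criterion.
- Keep mean GSRS as supportive, described as symptoms under the dose-adjustment rule, and replace the named time points with the biweekly schedule within 12 months.

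Reconcile three passages on follow-up after stopping drug. Section 3.5 withdraws a woman who cannot take it, section 4.10 lets her stay for assessments, and section 7.5.4 follows everyone to the end. Which GSRS scores exist after a stop depends on the answer.

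The cost is analysis wording and one table, since intolerance episodes and the GSRS data are already recorded in the CRF. No dose or clinical rule changes. The drawback is precision: at 40% versus 5%, the approximate 95% half-width is 1.96 × √(0.40 × 0.60/20 + 0.05 × 0.95/20) = 0.23, or 23 percentage points either side.

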4. STUDY DESIGN AND METHODS

4.1 Overview of the study: This will be a 12-month, double-blind, randomized, placebo-controlled trial of VSL#3 or placebo (**Figure 1**). Participants will be randomized to the placebo group or the VSL#3 group and treated and followed serially for 12 months. Baseline and follow-up assessments will be performed during an outpatient visit in the Emory University Hospital (EUH) Clinical Research Network (CRN) site of the Atlanta Clinical and Translational Science Institute (ACTSI) before initiation of the study drug (entry), and 6, and 12 months following baseline assessments. Subjects will report to the CRN after having fasted for at least 8 hours.

Figure 1: Study schema for protocol “Use of a Commercially Available Combination Probiotic, VSL#3, for Bone Health in Postmenopausal Women”

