An Institutional Review Board (IRB) approved study designee will provide verbal and written consent. The study is discussed thoroughly with each potential participant, and she will be encouraged to ask questions regarding the study and her participation. If the potential participant decides to enroll, she will sign the written informed consent, as will the study team member conducting informed consent. A copy of the signed consent form will be provided to enrolled study participants. Subjects must be able to read, write and understand the consent documents. Study personnel will subjectively assess the capacity to give informed consent through the use of questions to ensure understanding and comprehension of the study. Only adults will participate.

4.4. Study Initiation and baseline assessments: Following screening and informed consent, baseline assessment and laboratory evaluation will be performed as outlined in **Table 1**. Dietary calcium and vitamin D intake will be reviewed by a registered dietitian. For participants not meeting at least the Recommended Dietary Allowance (RDA) for calcium (1200 mg) and vitamin D (600 IU), a recommendation will be provided for sufficient over-the-counter calcium citrate and/or vitamin D3 to meet the RDA. Participants will be allowed to continue their current regimens; however, they will be asked not to begin any new supplement, medical, or exercise therapies that could influence bone health. For individuals with a screening 25(OH)D < 20, a study physician will communicate with the participant's primary MD (and/or the participant directly) and recommend a standardized dose of vitamin D replacement (daily vitamin D₃ dose of 5,000 IU daily + 50,000 IU weekly for 12 weeks with a recheck of 25(OH)D level in 3-4 months).

Table 1. Study Endpoints by Visit

Assessments	Screen in clinic or CRN unit	Entry visit in CRN unit (max 4 weeks after screen visit)	6 mo visit in CRN unit (+/- 1 month)	12 mo visit in CRN Unit (+/- 1 month)
Medical/Surgical history, medication use, dietary calcium intake, alcohol intake, physical activity	x		x	x
Serum FSH (if indicated)	x			
Physical Exam	x		x	x
Concomitant medications	x	x	x	x
Gastrointestinal Symptom Rating Scale (GSRS)		Determine GCRS every 2 weeks 		
Study drug adherence assessment		Determine adherence every 2 weeks 		
Fasting serum markers of bone turnover (CTX and PINP)		x	x	x
Serum RANKL (free), OPG, TNF, IL-17		x	x	x

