DXA scan: (lumbar spine, femoral neck, and total hip, total and regional body fat, total and regional lean body mass, visceral fat)*	x	x		x
Dietary Intake 3-day food record		x	x	x
BioElectrical Impedance Analysis (BIA) Body composition and total body water		x	x	x
Anthropometrics (height, weight, BMI, waist & hip circumference)				
Handgrip strength Hand-held dynamometer		x	x	x
Serum 25(OH)D	x			x
Stool microbiota composition		Xx	Xx	Xx
Plasma metabolomics		x	x	x
Plasma Amino thiols (GSH, GSSG, Cys, CySS)		x	x	x
Serum Intact PTH	x			
Complete blood count (CBC)	x		x	x
Chemistry profile	x		x	x
Urinalysis	x		x	x

*Note: First DXA scan will be done at the screening visit or the entry visit (not both).

4.5 Intervention: A total of 40 matched postmenopausal women meeting all specific inclusion/exclusion criteria will be blindly randomized to one of two study arms. **Arm A** (n=20): VSL#3 two active sachets [containing 450x10⁹ colony-forming units (CFU)/sachet], taken daily in a single administration; **Arm B** (n=20; control): two placebo sachets taken daily in a single administration. Thus, Arm A will receive 900 billion CFU daily and the control group (Arm B) will receive no supplemental probiotics (**Figure 1**).

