- **Handgrip strength:** A small, handheld dynamometer will be used to measure grip strength. Participants will be asked to squeeze the instrument as hard as they can for 3 seconds, which will measure the pounds of force applied.
- **Questionnaires:** Participants will be asked to answer a standardized, validated questionnaire (15 questions) about GI symptoms segregated into 5 symptom domains (see below). They will also complete a questionnaire assessing their habitual physical activity (Modified Baecke Questionnaire)²⁰.

4.9. Primary Endpoint: The **primary endpoint is** change in BMD of the lumbar spine (L1-L4 segment), as measured by DXA.

4.10 Secondary Endpoints (please see Table 1 above): Serial measures of: 1) bone density of the non-dominant hip (femoral neck and total hip area) as measured by DXA, 2) serum collagen type 1 cross-linked C-telopeptide (CTX) concentrations (a marker of bone resorption), 3) serum procollagen type I N propeptide (PINP) concentrations (a marker of bone formation), 4) serum free receptor activator of nuclear factor kappa-B ligand (RANKL) concentrations, 5) serum osteoprotegrin (OPG) concentrations, 6) serum tumor necrosis factor- α (TNF α), 7) serum interleukin-17 (IL-17) concentrations, 7) total and regional body fat (including visceral fat) and lean body mass as measured by DXA and BIA, 8) plasma thio/disulfide redox biomarkers, 9) compliance with study drug administration 10) overall study recruitment and retention, and 11)) **stool microbiota composition**. Measurements of indices of bone turnover and cytokine levels will provide much needed mechanistic information to establish whether VSL#3 may prevent bone loss and/or increases bone mass by regulating bone resorption, formation, or both. Based on animal data, we hypothesize that treatment with VSL#3 will quickly decrease bone resorption and then stimulate bone formation.

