5. DRUG DOSING

5.1. Method for determining doses: Doses were based on the concentration of colony forming units (CFU) within a single, commercially available sachet, and doses used in previous trials in adults with inflammatory bowel diseases (IBD), irritable bowel syndrome, and other gastrointestinal (GI) disorders²⁵⁻³¹.

5.2. Maximum Dosage: The maximum dosage will be 900x10⁹ CFU orally daily. This or higher doses have been used in most trials designed to assess the tolerability and efficacy of VSL#3 in IBD and irritable bowel syndrome in adults.

5.3. Drug duration: Patients will take the drug for 1 year.

5.4. Distribution and Storage of Investigational Products: The study drug/placebo will be delivered to the EUH Investigational Drug Service (IDS) directly from the manufacturer. The EUH IDS will store the study drug/placebo under the appropriate storage conditions, as indicated by the manufacturer. The Pharmacy will dispense the study drug/placebo to study subjects (who will remain blinded). Subjects will be provided with sufficient study drug product every two months. IDS will dispense a 2-month supply of the study drug sachets to the study team for each subject serially, who will over-night mail the resupply with a commercial carrier in sealed Styrofoam containers containing cold packs. The IDS will provide subjects with instructions for study drug storage at home. For all products provided, the lot number and expiration date will be recorded in individual subjects case report forms. All study drug products will be labeled with the following, "Caution: New Drug—Limited by Federal (United States) law to investigational use."

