8. INCIDENTAL FINDINGS

Subjects will be receiving a DXA scan at screening/entry and again at 12 months for research purposes only. The scans will not be used for clinical or diagnostic purposes. If a potential subject is screened and found to have a T-score ≤ -2.5 , in the lumbar spine, femoral neck or total hip as measured by DXA, the individual will be provided with a referral to an endocrinologist and/or primary care physician and will have an option to have the scan sent directly to the physician of choice for review. The DXA procedure generates a report that includes bone mineral density of the spine and hip. For enrolled study participants, they will be given their 12-month DXA report, and they will be encouraged to share this information with their healthcare providers in making a diagnosis about the state of her bones. For enrolled subjects found to have a 12-month T-score ≤ -2.5 , in the lumbar spine, femoral neck or total hip as measured by DXA, the individual will be provided with a referral to an endocrinologist and/or primary care physician and will have an option to have the scan sent directly to the physician of choice for review. Study participants may receive a copy of DEXA results on their 12 month study visit. They will be reminded that the DEXA scan is for research only, and participants will be encouraged to share the results with their healthcare provider.

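### Section 4.14 builds the repeated-measures model on baseline, 1 year and 2 years in a 12-month trial: the 2-year level can hold no data, the 6-month visit is missing, and the GSRS assessment times are not named

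*Combined protocol and SAP*

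**What the plan says.** Section 4.14 specifies one repeated-measures means model in SAS MIXED, with arm, time and their interaction, and says it will yield "separate estimates of the means by time on study (baseline, 1-year and 2-years) and treatment group". The sentence applies to every outcome, but the bracket after it names only the GSRS scale scores and BMD. The interaction is the primary overall test. If there is no interaction, the treatment main effect becomes the primary test of efficacy.

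The schedule elsewhere is different:

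- Section 4.1 places assessments before study drug starts "and 6, and 12 months following baseline assessments".
- Section 5.3: "Patients will take the drug for 1 year".
- Section 7.3: the last contact is a safety telephone call one month after study drug stops.
- Section 8: "Subjects will be receiving a DXA scan at screening/entry and again at 12 months for research purposes only". The footnote to Table 1 adds: "First DXA scan will be done at the screening visit or the entry visit (not both".
- Table 1 schedules CTX, PINP, free RANKL, OPG, TNF, IL-17, plasma aminothiols, metabolomics, stool microbiota, BIA and handgrip strength at entry, 6 and 12 months.
- Section 4.10 has the GSRS collected every two weeks, in person at baseline, 6 and 12 months and otherwise by telephone. It names five domain scores and a total for analysis.

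Section 4.10 also states the mechanistic hypothesis: "we hypothesize that treatment with VSL#3 will quickly decrease bone resorption and then stimulate bone formation".

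**The concern.** A time factor in a means model has to match the visits at which the outcome is measured. Here one of the three listed levels lies a year beyond the end of follow-up, and a visit that does take place has no level.

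For the markers, the missing visit is the only one between entry and 12 months. It is therefore the only direct evidence in the trial on whether resorption changes before formation, although a single intermediate sample is limited evidence on that order. An arm difference present at 6 months and gone by 12 would be invisible to the listed time points.

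For the GSRS, the scales are fixed but the assessment times are not. The listed levels match only two of the roughly 27 planned scores per woman. An analyst who sets the list aside has to choose among the rest without a pre-specified rule.

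**Working it through.** **1. The plan's own figure.** Section 4.13 claims more than 85% power for a 0.03 g/cm² difference in change, with SD 0.03, 20 per arm, two-sided 5% and a two-sample t-test. The noncentrality is 0.03 / (0.03 × √(2/20)) = 3.162 on 38 df, which gives 86.9%. The figure reproduces. (Whether 0.03 is the right SD is a separate question.)

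**2. BMD under the listed levels.** Two arms by three levels is 6 mean parameters. With data only at baseline and 12 months the design matrix has rank 4. Neither arm's 2-year mean is estimable, and the interaction has 1 df instead of 2. That 1-df interaction is the comparison of 12-month change between arms, so power at the plan's inputs stays at 86.9%.

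**3. Marker data used.** Planned: 40 women × 3 visits = 120 values per marker. Usable under the listed levels: 40 × 2 = 80. Dropped: 40, or one third. With levels 0, 6 and 12 months the design has full rank 6 and a 2-df interaction.

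**4. Illustration: a difference at 6 months only (interaction test).** The documents give no marker effect size or correlation, so these are assumptions: SD 1, difference d at 6 months and none at 12, equal correlation ρ between visits, complete Gaussian data, 20 per arm.

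- *Baseline and 12 months only:* the true difference in change is zero, so the rejection rate is the 5% level.
- *Three visits:* for the changes from baseline to 6 and to 12 months, the covariance matrix is (1−ρ) × [[2,1],[1,2]]. The Hotelling noncentrality is (20/2) × d² × 2 / [3(1−ρ)], referred to F with 2 and 37 df (critical value 3.25). For d = 0.8 and ρ = 0.5 it is 10 × 0.64 × 2 / 1.5 = 8.53, which gives 71.0%.

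| d (SD) | ρ = 0.3 | ρ = 0.5 | ρ = 0.7 |
|---|---|---|---|
| 0.5 | 24.4% | 32.9% | 51.4% |
| 0.8 | 55.4% | 71.0% | 91.0% |
| 1.0 | 75.9% | 89.1% | 98.7% |

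**5. A difference that persists.** If the 0.8 SD difference is equal at 6 and 12 months (ρ = 0.5), the interaction test has 69.3% power with two time points (noncentrality 0.8 / √(2/20) = 2.53) and 71.0% with three. Section 4.14 goes further, though, because it falls back on the main effect when there is no interaction. Simulating either test being positive, with the robust standard errors uncorrected for small samples, gives about 80% with two times and 89% with three. The same procedure is positive under the null about 10.8% and 12.2% of the time, so part of that gap is inflation.

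**6. GSRS.** Every two weeks for 52 weeks gives 26 contacts, or 27 with baseline. Read as twice monthly, a term the protocol also uses, it is 24 and 25. The listed levels match 2 of these.

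**The case against.** The strongest reply is that this is an evident slip. Sections 4.1, 4.10 and 5.3 and Table 1 all point to 6 and 12 months, no one could fit a 2-year mean, and software would drop the empty level. That is largely right, and it is why the point is minor. It does not settle the GSRS times, and no passage corrects the list.

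A second reply is that Section 4.14 names only the GSRS and BMD, so the list may not govern the markers at all. That stands as a genuine ambiguity. On the narrow reading the markers lose no data, but they then have no stated model, which needs correcting too.

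A third is that the power contrast uses an effect size and pattern the documents do not supply, and covers only the first of the two tests in Section 4.14. Both are true. The contrast shows what the literal list cannot see; it is not a forecast of what the trial will miss.

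Three stronger readings are tempting, and the documents support none of them:

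- *The primary analysis is compromised.* BMD is measured only at two times, and both are in the list. The 6-month BMD values in Section 4.13 belong to the planning dataset of 380 women.
- *A second year of follow-up was intended.* Nothing outside this one phrase suggests it.
- *All two-weekly GSRS scores will go into one many-level interaction test.* Section 4.14 lists three levels and proposes no such test.

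**Conclusion.** Wrong as written; minor. The time list in Section 4.14 contradicts the trial's 12-month schedule, contains a level that cannot be filled, and omits the 6-month visit. The primary BMD interaction test, and the power stated for it, do not change.

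The marker consequence depends on two conditions: that the model extends beyond the two outcomes named in the bracket, and that the list is followed literally. If both hold, one third of the planned values per marker are lost, and a difference confined to 6 months could be detected only by chance (about 5%, against 55% to 91% under the 0.8 SD assumptions above). For a persistent difference the interaction test loses little, but that reassurance does not extend to the full two-step procedure.

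For the GSRS, what is open is which assessments enter the model. The scales themselves are already named.

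**What to change.** Before unblinding, replace the single time list in Section 4.14 with one by outcome, and say explicitly that the model covers the secondary markers (or give them their own):

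- BMD and DXA body composition: baseline and 12 months.
- Turnover markers, cytokines, redox markers, metabolomics, stool microbiota, BIA and handgrip strength: baseline, 6 and 12 months.
- GSRS: name the assessments that enter. Examples are the in-person baseline, 6- and 12-month scores, or a baseline-adjusted arm difference in mean on-treatment score for the total and each domain.

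The cost is SAP wording and programming; no visit, sample or patient is added. The mean on-treatment GSRS contrast is less sensitive to a transient early difference, which a descriptive plot by time can show.
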